6.5 Caregiver Interview

in the caregiver diary.

An optional qualitative interview with caregivers of study subjects will be conducted remotely by telephone. Only caregivers of subjects for whom separate informed consent for the caregiver interview is completed will be interviewed. Interviews will be conducted by trained moderators from a 3rd party and are anticipated to be approximately up to 60 minutes in duration. The interviews are planned to elicit a better understanding of the observable signs as well as the impact of study drug and RTT both on the study subject and on the caregiver. The interviews will document changes observed by the caregivers over the course of participation in the study. The interviews will also provide an opportunity to describe the meaningfulness of any improvements that may have occurred from the perspective of the caregiver. Interviews will be audio-recorded and transcribed for analysis. Any personally identifiable health information mentioned during the interview will be redacted by the interviewer prior to transcription of the interview. Furthermore, if any potential adverse events are revealed during the interview, the interviewer will inform the investigator of the potential adverse event. Audio recordings of the interviews will be destroyed following transcription.

Following the analysis of the qualitative data, a summary report that describes the objectives, methods, participants, and results of the qualitative interviews will be prepared and reported separately from the clinical study report.

The caregiver interview will be administered during Treatment Period B, at or before the final study visit (Week 104 [EOT/ET]).

6.6 Pharmacokinetic Assessments

PK blood samples will be collected at each visit during Treatment Period A.

At the Baseline visit, a PK sample is drawn predose. After the first dose of study drug is administered, two PK samples will be collected: the first, 2 hours (±15 minutes) after dosing, as close as possible to the postdose ECG, and the second, at least 1 hour after the first.

Final Version: 1.0

In addition to the two PK samples taken at Baseline, two PK samples will be taken at each subsequent visit (or upon early termination [ET]) in Treatment Period A, for a total of ten postdose PK samples over the duration of the study. At Visit 3, Visit 4, Visit 5, and Visit 6, the two PK samples will be collected at one of the following time intervals:

- 1-3 hours after dosing
- 4-7 hours after dosing
- 8-11 hours after dosing

Every subject should provide at least two PK samples from each of the specified time intervals over the course of Visits 3 through 6 (1-3 hours after dosing, 4-7 hours after dosing, and 8-11 hours after dosing). The two PK samples taken within a time interval should be collected at least one hour apart.

Pharmacokinetic samples will also be collected, if possible, at any ET visit during Treatment Period A, or the visit immediately following any SAE, or following any AE leading to discontinuation.

Pharmacokinetic samples will not be collected at the Week 104 visit, or at an ET visit during Treatment Period B.

For all scheduled PK samples (and for unscheduled samples if possible), the dates and times of administration of the study drug over the 2 days prior to and on the morning of the PK sample draw, as well as the date and time of the sample draw, will be recorded. For samples collected from subjects who experience any SAE or experience an AE leading to discontinuation, the date and time of the last dose of study drug prior to the SAE or AE leading to discontinuation will also be recorded.

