1.3.1.1 Linearity and Dose Proportionality

Trofinetide exhibits linear kinetics with no time- or dose-dependent effect on PK parameters. Systemic exposure to trofinetide was dose-proportional across the studied dose range, with no metabolic auto-inhibition or auto-induction.

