Study drug will be dispensed at the site during the Baseline visit when the visit is conducted in the clinic. For the remainder of the study, investigational product will be shipped directly to the subject. Study drug shipment, return, and accountability will be performed in accordance with the drug distribution plan.

Subjects Enrolled Under Protocol Amendment 1 Dated 30 June 2021

Subjects will begin treatment with trofinetide 2 g (in 10 mL) BID (Table 5–2). The dose will be increased to 4 g (in 20 mL) BID at the Week 2 visit. At the Week 4 visit, the dose will be increased to 5 g (in 25 mL) BID for subjects who weigh ≥9 to <12 kg, or 6 g (in 30 mL) BID for subjects who weigh 12 to <20 kg. In each case, the dose will be increased only if the Investigator judges that the subject is showing acceptable tolerability of the treatment. An ECG must be performed 2 hours (±15 minutes) after the first dose, and a PK sample is to be taken as close as possible to the postdose ECG. A second PK sample will be taken at least 1 hour after the first PK sample.

Table 5–2 Dosing Schedule for Trofinetide, Based on Weight at Baseline, for Subjects Who Enrolled Under Protocol Amendment 1 Dated 30 June 2021

Dose Commences (Visit)	Weight at Baseline	Dose	Total Daily Dose	
Day 1 ^a	All subjects	10 mL (2 g) BID	20 mL (4 g)	
Week 2 (Visit 3)	All subjects	20 mL (4 g) BID	40 mL (8 g)	
Week 4 (Visit 4)	\geq 9 to <12 kg	25 mL (5 g) BID	50 mL (10 g)	
	12 to <20 kg	30 mL (6 g) BID	60 mL (12 g)	

^a The first dose of study drug will be administered after all Baseline assessments are completed, or, if the Investigator judges that it is too late in the day, on the following day. The day the first dose is taken will be considered Day 1.

Study drug is administered twice a day, once in the morning and once in the afternoon or evening. There should be at least 8 hours between doses.

At any point in the study, if the subject is not able to tolerate administration of the assigned dose, the Investigator may instruct the caregiver to reduce the dose of study drug to a dose as low as 1 g BID. In addition, up to four doses (in total, consecutive or non-consecutive) may be withheld within the first 6 weeks.

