9.2 Statistical Hypotheses

This is an open-label and single arm study. All statistical analyses will be descriptive. No statistical hypothesis will be tested.

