9.3 Sample Size Determination

Approximately ten (10) to fifteen (15) subjects will be enrolled in this study, at least 1 subject who weighs ≥9 to <11 kg, and at least 4 subjects who are less than 4 years of age at Screening, including at least one subject who is 2 years of age. The sample size is not based on statistical considerations and is believed to be adequate to characterize the PK of trofinetide in this population.

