16. CLINICAL PHARMACOKINETIC AND PHARMACODYNAMIC ANALYSES

For trofinetide-treated subjects, whole blood concentration for trofinetide will be listed. Whole blood concentration data for trofinetide will be summarized for the PK Analysis Set at each analysis visit using descriptive statistics. Concentrations that are below the limit of quantification (BLQ) will be displayed as “BLQ” in the data listings and imputed as 0 for computing summary statistics.

If data allow, population PK and PK/PD analyses will be performed to further characterize the PK profile and exposure response relationship of trofinetide using measures of safety and efficacy parameters. The results of population PK and PK/PD modeling will be presented in a separate report.

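### SAP 16 averages trofinetide concentrations by visit across different doses and postdose windows, and protocol 6.6 does not tie the amount taken to each PK sample

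*Protocol*

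**What the plan says.** - **Concentration table.** SAP 16: "Whole blood concentration data for trofinetide will be summarized for the PK Analysis Set at each analysis visit using descriptive statistics". SAP 5.1 pools all subjects into a single total group for tables. Neither section splits by dose or by time after dose.
- **Sampling.** Protocol 6.6 takes two postdose samples at Baseline ("After the first dose of study drug is administered, two PK samples will be collected") and two at each of Visits 3 to 6, "for a total of ten postdose PK samples over the duration of the study". At each of Visits 3 to 6 a girl's pair falls in one of three windows after dosing: 1-3, 4-7 or 8-11 hours. Which window goes with which visit is not fixed.
- **Dosing record tied to the sample.** Protocol 6.6 asks for "the dates and times of administration of the study drug over the 2 days prior to and on the morning of the PK sample" draw, together with the draw time. It names no amount.
- **Titration.** Protocol 5.1.3.1: "The dose will be increased to 4 g (in 20 mL) BID at the Week 2 visit". At Week 4 the scheduled dose becomes 5 g or 6 g BID according to weight at Baseline. Each step depends on the investigator's view of tolerability, and reductions are allowed. SAP 3.1 states that all subjects follow this schedule, so the titration in the original protocol does not apply.
- **Other dosing records.** Protocol 6.4 has study drug dosing, and missed or partial doses, entered in the caregiver diary. SAP 11.2 uses dose-modification data from the eCRF and the modified prescribed schedule held in the EDC.
- **Pharmacology.** Protocol 1.3.1.1: "Systemic exposure to trofinetide was dose-proportional across the studied dose range". Protocol 1.3.1.6 gives an effective half-life of about 1.2 hours and a terminal half-life of about 13 hours.

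**The concern.** Protocol 2.1.1 makes whole blood concentration a primary PK endpoint. Protocol 1.4.1 says the PK data should show what exposure the doses reached will produce, for comparison with older patients. A by-visit mean cannot show this when the girls at that visit have taken different doses and been bled in different windows.

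The table could be split by dose only if the dose before each draw is known. Visits 3 and 4 are both PK days and scheduled step days, and the step is conditional. The visit number therefore does not tell the analyst whether the last dose was the old one or the new one. With a dose-proportional drug, attaching the wrong one distorts the dose-normalised concentration by the full ratio of the two doses.

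**Working it through.** There is no power calculation to reproduce: "No statistical hypothesis will be tested" (protocol 9.2), and "The sample size is not based on statistical considerations" (protocol 9.3). The stated figure that can be checked is the sample count.

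**1. Samples on step days** (protocol 6.6 and 5.1.3.1)
- Postdose samples per girl: 2 + 4 visits × 2 = 10, which agrees with the protocol.
- On scheduled step days (Visits 3 and 4): 2 × 2 = 4, and 4/10 = 40%.
- If every sample is drawn: 40 of 100 with 10 girls, 60 of 150 with 15.

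**2. Size of each step**
- Week 2: 4/2 = 2.0. This applies to 2 of the 10 samples.
- Week 4: 5/4 = 1.25 or 6/4 = 1.5, by weight group. This applies to another 2 of the 10.
- Weeks 8 and 12: no scheduled step. The scheduled doses differ between girls by 6/5 = 1.2.

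**3. What a mixed-dose mean represents.** Suppose a share p of the Week 2 samples follow 4 g and the rest 2 g, at equal times after dose. Under dose proportionality, the visit mean is (1 + p) times the 2 g mean. The documents do not give p, so the multiplier can lie anywhere from 1.0 to 2.0. At p = 0.5 it is 1.5, which corresponds to 3 g, a dose that is not in SAP Table 1.

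**4. What mixing the windows does.** I take the window midpoints (2, 5.5 and 9.5 hours) as an assumption. Protocol 1.3.1.3 puts the peak at about 2 hours. The concentration relative to 2 hours is 0.5^(Δt / half-life):

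| Time | Half-life 1.2 h only | Half-life 13 h only |
|---|---|---|
| 5.5 h (Δt = 3.5) | 0.13 | 0.83 |
| 9.5 h (Δt = 7.5) | 0.013 | 0.67 |

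Decline is biphasic and the weight of each phase is not given, so the truth lies between the columns. Even at the slow end, the late window sits a third below the early one.

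**5. Why the last dose is the one that counts.** On the 1.2-hour half-life, what remains of a dose is 0.5^(8/1.2) ≈ 1% at 8 hours and 0.5^(12/1.2) ≈ 0.1% at 12 hours. The terminal phase retains more of its own component (65% and 53%), but protocol 1.3.1.2 reports little or no accumulation.

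**6. Whether returned-bottle volumes could fill the gap.** The 2 g and 4 g doses differ by 20 − 10 = 10 mL. SAP Table 3 reads volume in 0.5 cm steps of about 18 mL, so accountability data cannot identify a single dose.

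**The case against.** **The amount is recorded elsewhere.** This largely stands. A reader might infer from protocol 6.6 that the dose taken is never captured, but the diary and the EDC dose-modification data contradict that. What remains is that neither document connects those records to the PK samples. The eCRF pages and laboratory manual are not available and may already make the link. For the same reason, the documents do not support a claim that the prescribed-dose record cannot tell the old dose from the new one on a step day.

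**The step-day ambiguity is limited.** This stands in part. Dose times and draw times are recorded, and doses before the investigator's decision should be at the old level. The unclear case is a visit-day dose whose order relative to that decision is not recorded.

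**SAP 16 does not pool every dose in the study.** Correct. It works visit by visit, both Baseline postdose samples follow the 2 g first dose, and individual concentrations are listed. The mixing is within a visit, from Week 2 on.

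**Larger error figures are not supported.** A reader might apply the two-fold ratio to all four step-day samples, but it belongs to Week 2 alone. A reader might also divide 6 g by the lowest permitted 1 g and report a six-fold error at Weeks 8 and 12. That is a range of permitted doses, not an error in the recorded dose, and prescribed reductions are recorded.

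**Population PK carries the characterisation.** Protocol 9.5.3 assigns it to a separate plan that is not available and may bring in dose amounts. Other visits would also inform each girl's clearance, so an error at one visit would not pass through in full. This limits the point about protocol 6.6. It does not rescue the SAP 16 table, which is the stated summary of a primary endpoint.

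**Route.** Doses may go by mouth or gastrostomy tube, but the documents give no evidence that route changes exposure. Recording it is optional.

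**Conclusion.** The point holds in two parts of unequal strength.

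The firmer part is the SAP 16 table. From Week 2 on, each visit summary can combine doses that differ by up to 2.0-fold at Week 2, 1.5-fold at Week 4 and 1.2-fold at Weeks 8 and 12 on the scheduled titration alone, and more where a dose was withheld from escalation or reduced. It also combines windows whose concentrations differ further. This rests on dose proportionality holding in this age group, and on girls being sampled in different windows at the same visit, which protocol 6.6 allows but does not require.

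The weaker part is the record in protocol 6.6. The text does not tie the amount taken to the sample, and for 4 of 10 postdose samples the visit alone leaves the preceding dose open. This is an unstated link. The documents do not show that the data are missing or that any concentration has been matched to the wrong dose.

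**What to change.** **SAP 16.** Summarise concentration by the actual preceding dose level and by time-after-dose window, and add a dose-normalised column. Apply the same layout at the interim, since SAP 17 runs Section 16 there too.

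**Protocol 6.6 and the PK eCRF page.** For the last dose before each draw, record the volume actually taken, including whether it was partial or vomited, or state that it will be linked from the diary. State that each sample is matched to that dose. Where visits are already past, reconcile from the diary where it was kept. None of this alters the dosing rules.

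**Cost.** One table layout, a few fields or a linkage step, and some reconciliation; no extra blood or visits. The real drawback is thin cells. With 10 to 15 girls a visit yields 20 to 30 samples. Spread evenly over two doses and three windows, that is 20/6 ≈ 3 to 30/6 = 5 per cell. Because protocol 1.3.1.1 reports no time dependence, dose-normalised values could be combined over Visits 3 to 6 within each window. Protocol 6.6 asks for at least two samples per girl per window, so each window would then hold at least 2 × 10 = 20 to 2 × 15 = 30 samples.

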6.6.1 Blood Sampling

Table 6–1 tabulates the maximum allowable blood collection volumes by weight for affected children and Table 6–2 summarizes the blood volumes to be drawn in the present study in both a 24-hour and a 30-day period. The total amount of blood to be obtained from each subject should not exceed the allowable limits for affected children.

Each PK sample requires collection of 2 mL of venous blood. A total of three 2-mL venous blood samples will be collected for PK sampling from each subject at the Baseline visit for the measurement of trofinetide concentrations in blood (Table 6–2). A total of two 2-mL venous blood samples will be collected from each subject on each subsequent day of PK sampling.

Study: ACP-2566-009 Clinical Study Protocol Amendment 2 Date: 19 December 2022

When possible, an additional PK sample will be collected from subjects who experience any SAE or experience an AE leading to discontinuation as soon as possible after the occurrence of that event (see Section 7.4.2).

Additional information for specimen preparation, handling, storage and shipment is provided in Section 6.6.2.

Blood Collection Volume Limits in Affected Children Table 6–1

Weight	9 kg	10 kg	11 kg	12 kg
Maximum allowable blood volume in a 24-hour period	18 mL	20 mL	22 mL	24 mL
Maximum allowable blood volume in a 30-day period	36 mL	40 mL	44 mL	48 mL

Sources: North Shore LIJ Human Subject Protection Program Guidance Document, Maximum Blood Draw Limits, Version 11/24/14

Note: Subjects must weigh ≥9 kg and <20 kg at Screening.

Table 6-2 Blood Collection Volumes for MECP2 Mutation Testing, Safety **Labs and Pharmacokinetic Samples**

	Screening Visit	Baseline Visit ^a	Visit 3 (Week 2)	Visit 4 (Week 4)	Visit 5 (Week 8)	Visit 6 (Week 12)	
Testing for MECP2 Mutation (if necessary)	3.0 mL						
Safety Labs							
Chemistry and TSH/free T3/free T4	3.7 mL						
Chemistry		2.2 mL	2.2 mL	2.2 mL	2.2 mL	2.2 mL	
Hemoglobin/reticulocyte	1.2 mL	1.2 mL	1.2 mL	1.2 mL	1.2 mL	1.2 mL	
Pharmacokinetic Samples							
Predose		2.0 mL					
Postdose		4.0 mL	4.0 mL	4.0 mL	4.0 mL	4.0 mL	
Total volume in any 24-hour period	7.9 mL	9.4 mL	7.4 mL	7.4 mL	7.4 mL	7.4 mL	

Final Version: 1.0

Table 6–2 Blood Collection Volumes for *MECP2* Mutation Testing, Safety Labs and Pharmacokinetic Samples (Continued)

Total volume in any 30-day period						
Screening and Baseline	17.3 mL					
Screening, Baseline, and Week 2	24.7 mL					
Baseline, Week 2, and Week 4		24.2 mL				
Week 4 and Week 8				14.8 mL		
Week 8 and Week 12					14.8	mL

Abbreviations: TSH=thyroid stimulating hormone; T3=triiodothyronine; T4=thyroxine

6.6.2 Specimen Preparation, Handling, Storage, and Shipment

An indwelling intravenous cannula may be used for collection of serial PK blood samples (saline is to be used to flush the indwelling cannula); otherwise, PK blood samples will be obtained via standard venipuncture procedures. Pre-prepared PK sampling tubes will be provided to each site within the lab visit kits for collection and storage of PK samples. Blood samples will be processed for determination of trofinetide whole blood concentrations (and of concentrations of possible metabolites identified).

At each time point, blood will be collected, processed as appropriate, and samples will be shipped to the central laboratory for storage and to the bioanalytical laboratory for analysis. The date and actual time of PK blood collection must be collected and recorded in the subject's eCRF. Each label will state the study number, subject number, analyte (whole blood), study day, and scheduled sample time.

A laboratory manual will be provided for sample processing, storage, and shipping procedures.

7 ADVERSE EVENTS

7.1 Specification of Safety Parameters

7.1.1 Definition of Adverse Event

An AE is defined as "any untoward medical occurrence in a patient or clinical study participant, temporally associated with the use of study drug, whether or not considered related to study drug".

An AE can therefore be any unfavorable and unintended sign (e.g., an abnormal laboratory finding), symptom, or disease temporally associated with the use of a drug, without any judgment about causality or seriousness. An AE can arise from any use of the drug (e.g.,

^a Baseline visit may take place over 2 days (see Section 3.1.2).

off-label use, use in combination with another drug) and from any route of administration, formulation, or dose, including an overdose.

A suspected adverse reaction is any AE for which there is a reasonable possibility that the drug caused the AE.

AEs do not include the following:

- Stable or intermittent chronic conditions (such as myopia requiring eyeglasses) that are present prior to Baseline and do not worsen during the study
- Medical or surgical procedures (e.g., surgery, endoscopy, tooth extraction, transfusion). The condition that leads to the procedure is an AE if not present at Baseline.
- Overdose of concomitant medication without any signs or symptoms unless the subject is hospitalized for observation; if an overdose occurs, it will be reported on an overdose form.
- Hospitalization for elective surgery planned prior to study (situation where an untoward medical occurrence has not occurred)

7.1.2 Definition of Serious Adverse Event

In addition to the severity rating, each AE will be classified by the Investigator as "serious" or "not serious." The seriousness of an event will be defined according to the applicable regulations and generally refers to the outcome of an event. An SAE is one that meets one or more of the following:

- Is fatal
- Is immediately life threatening
- Results in disability or permanent damage
- Requires hospitalization
- Prolongs existing hospitalization
- Is a congenital anomaly or birth defect (in an offspring)
- Is medically significant

Definition of Life Threatening

A life-threatening event places the subject at immediate risk of death from the event as it occurred. This does not include an AE, which, had it occurred in a more severe form, might have caused death.

Study: ACP-2566-009

Final Version: 1.0 Clinical Study Protocol Amendment 2 Date: 19 December 2022

Definition of Hospitalization

Hospitalization is defined by the Sponsor as a full admission to the hospital for diagnosis and treatment. This includes prolongation of an existing inpatient hospitalization.

Examples of visits to a hospital facility that do **not** meet the serious criteria for hospitalization include:

- Emergency room visits (that do not result in a full hospital admission)
- Outpatient surgery
- Preplanned or elective procedures
- Protocol procedures
- Social hospitalization, defined as admission to the hospital as a result of inadequate family support or care at the subject's primary residence

Definition of Disability or Permanent Damage

Disability is defined as a persistent or significant incapacity or substantial disruption of the ability to conduct normal life functions.

Definition of Medically Significant

Important medical events (medically significant events) that may not result in death, be life threatening, or require hospitalization may be considered to be an SAE when, based upon appropriate medical judgment, they may jeopardize the subject or may require medical or surgical intervention to prevent one of the outcomes listed in this definition. Examples of such events are intensive treatment in an emergency room or at home for allergic bronchospasm, blood dyscrasias, or convulsions that do not result in hospitalization or development of drug dependency or drug abuse.

An SAE may also include any other event that the Investigator or Medical Monitor judges to be serious or that suggests a significant hazard, contraindication, side effect, or precaution.

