4.2 Exclusion Criteria

A subject must meet none of the following exclusion criteria to be eligible for the study:

Concomitant Treatment

- 1. Has been treated with growth hormone within 12 weeks of Baseline
- 2. Has been treated with IGF-1 within 12 weeks of Baseline
- 3. Has been treated with insulin within 12 weeks of Baseline

Medical Conditions Other Than RTT

- 4. Has current clinically significant cardiovascular, endocrine (such as hypo- or hyperthyroidism, Type 1 diabetes mellitus, or uncontrolled Type 2 diabetes mellitus), renal, hepatic, respiratory or gastrointestinal disease (such as celiac disease or inflammatory bowel disease) or has major surgery planned during the study
- 5. Has a history of, or current, cerebrovascular disease or brain trauma
- 6. Has significant, uncorrected visual or uncorrected hearing impairment
- 7. Has a history of, or current, malignancy

Laboratory Studies, Vital Signs, and Electrocardiogram

- 8. Has one or more clinical laboratory test value(s) outside the range specified below at Screening:
 - a. hemoglobin value below the normal range
 - b. aspartate aminotransferase (AST) or alanine aminotransferase (ALT) value more than 1.5 × the upper limit of the normal range (ULN) for that subject's age and gender
 - c. total bilirubin value $\geq 1.5 \times ULN$
 - d. serum creatinine ≥ULN
 - e. serum potassium below the normal range; serum potassium may be repeated during the Screening period with the agreement of the Medical Monitor
 - f. thyroid stimulating hormone (TSH) value outside the normal range

9. Has a clinically significant abnormal laboratory value at Screening. Laboratory testing may be repeated during the Screening period with agreement of the Medical Monitor.

- 10. Has clinically significant abnormality in vital signs at Screening or Baseline
- 11. Has any of the following:
 - a. QTcF interval of >450 ms at Screening or Baseline
 - b. History of a risk factor for torsades de pointes (e.g., heart failure or family history of long QT syndrome)
 - c. History of clinically significant QT prolongation that is deemed to put the subject at increased risk of clinically significant QT prolongation
 - d. Other clinically significant finding on ECG at Screening or Baseline

Other Criteria

- 12. Has a significant sensitivity or allergic reaction to trofinetide or its excipients
- 13. Has participated in another interventional clinical study within 30 days prior to Screening

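### The elective-procedure exemption in Protocol 7.1.2 lacks the qualifier used in 7.1.1, so the seriousness of an elective admission prompted by an on-study event is left to discretion

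*Protocol*

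**What the plan says.** Protocol 7.1.2 sets out seven criteria, any one of which is enough: "An SAE is one that meets one or more of the following". Requiring hospitalization is one of them. "Hospitalization is defined by the Sponsor as a full admission to the hospital for diagnosis and treatment". A list then follows, introduced by "Examples of visits to a hospital facility that do" and continuing that they do not meet this criterion. One entry reads, in full, "Preplanned or elective procedures".

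Protocol 7.1.1 lists what is not an AE. Three of its bullets matter here:
- Stable or intermittent chronic conditions present before Baseline are excluded, provided that they do not get worse during the study.
- Procedures are not AEs, but: "The condition that leads to the procedure is an AE if not present at Baseline".
- The admission exemption is: "Hospitalization for elective surgery planned prior to study (situation where an untoward medical occurrence has not occurred".

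Two other routes to seriousness remain in 7.1.2. The medically significant criterion says that an event may be considered an SAE when, on medical judgement, "they may jeopardize the subject or may require medical or surgical intervention to prevent one of the outcomes listed in this definition" applies. A closing sentence says that an SAE may also include any event that the Investigator or Medical Monitor judges to be serious.

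SAEs are one of the four primary safety endpoints (Protocol 2.1.1, SAP 15.1). SAP 15.2 tabulates treatment-emergent SAEs by SOC and PT.

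**The concern.** Two adjacent sections give different rules for the same kind of admission. Section 7.1.1 asks both when the surgery was planned and whether something untoward lay behind it. Section 7.1.2 asks neither. An investigator who applies 7.1.2 as written could class an elective admission as not serious even though a condition that arose or worsened on drug was the reason for it.

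The error can go only one way: the exemption removes SAEs and never adds them. The serious classification also does more than fill a table. Under 7.4.2 it triggers a report within 24 hours, a visit with the Investigator or designee as soon as feasible, and a blood sample for trofinetide concentration. A missed classification can lose safety oversight and PK data as well as a count.

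The procedure bullet in 7.1.1 adds a smaller problem. It names only conditions absent at Baseline, while the chronic-condition bullet above it also depends on worsening. These girls enter with chronic problems, so the worsening of an existing condition is a realistic case and both bullets should state it.

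**Working it through.** The plan states no figure on this point, so there is none to reproduce. The check is textual, with a small calculation for scale.

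**1. Does the 7.1.2 entry reach full admissions?** Yes. Outpatient surgery has its own entry, and another entry covers social hospitalization, which is defined as an admission. The list is therefore not confined to visits without admission. The emergency-room entry carries a qualifier (no full admission results); the elective-procedure entry carries none.

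**2. The two exemptions side by side.**

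| | 7.1.1 (not an AE) | 7.1.2 (not hospitalization) |
|---|---|---|
| Timing | planned before the study | preplanned *or* elective; no time limit |
| Cause | no untoward occurrence | silent |

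**3. An elective admission for a condition that arose on study.** Under the procedure bullet in 7.1.1 the condition is an AE. Under the literal text of 7.1.2 the admission does not meet the hospitalization criterion. Seriousness then turns on the two discretionary routes.

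**4. The same admission for a Baseline condition that worsened on study.** The chronic-condition bullet in 7.1.1 does not exclude it, because it worsened. Section 7.2.3 lets an AE start at a significant sustained worsening. Together these make it an AE. The procedure bullet is silent on worsening. Seriousness is as in step 3.

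**5. Can the analysis recover the event?** SAP 15.2 tabulates SAEs as they are recorded. SAP 5.10 and 5.11 impute missing severity and relationship; no rule concerns seriousness, and here the field would be filled in as not serious, not left missing.

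**6. Scale.** Inputs: N = 10 to 15 (Protocol 9.3), and, as an assumption, exactly one affected girl with no other SAE. The change in SAE incidence is 1/N:
- N = 10: 1/10 = 10.0 points
- N = 15: 1/15 = 6.7 points

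If hers were the only SAE in the study, the exact (Clopper-Pearson) 95% intervals would be:

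| N | Classed as serious | Classed as not serious |
|---|---|---|
| 10 | 1/10 = 10.0% (0.3 to 44.5) | 0/10 = 0% (0 to 30.8) |
| 15 | 1/15 = 6.7% (0.2 to 31.9) | 0/15 = 0% (0 to 21.8) |

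The documents give no frequency of elective admissions in this population, so no expected number of missed girls follows.

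**The case against.** The strongest reply is that this is a wording mismatch and that nothing need be lost. The entry is an example under one of seven criteria. It does not say that admissions caused by an AE are exempt; it is silent on cause, and 7.1.1 suggests that the narrower rule was intended. The medically significant criterion is broad enough to reach most events that need a procedure, and the Medical Monitor as well as the Investigator can call any event serious. A recorded AE still appears in the TEAE tables and the by-subject listing, weight changes of 7% or more are flagged separately (SAP Table 6), and a DSMB reviews the data (SAP 18).

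Much of this stands. It rules out several stronger readings that a reader might reach:

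- *That the SAE definition as a whole exempts these admissions.* It does not; only the hospitalization criterion is affected.
- *That a worsened Baseline condition leading to a procedure is not even an AE.* The procedure bullet does not say that a condition is an AE only if absent at Baseline, and the bullet above it points the other way.
- *That exclusion criterion 4 makes any later elective procedure a sign of deterioration.* The criterion excludes a girl who has a listed disease "or has major surgery planned during the study". It covers major surgery only and says nothing about why later procedures are done.
- *That one case would change a conclusion.* No hypothesis is tested (Protocol 9.2) and no SAE threshold is set.

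The reply does not remove the gap. Hospitalization is the criterion that makes an event serious without a further judgement about its importance, and the literal text replaces it with routes that the Investigator may take. The listing fields named in SAP 15.2 do not include hospital admission, so a reader of the listing may not see that one occurred.

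**Conclusion.** The point holds as an inconsistency between 7.1.1 and 7.1.2 in which the 7.1.2 rule is too broad. SAE incidence *can* be biased low, and the 7.4.2 report and PK sample *can* be missed; neither is automatic. The size is 6.7 to 10 percentage points for each girl affected. This rests on 10 to 15 treated girls, on her having no other SAE, and on neither discretionary route being used. How often this would happen cannot be derived from the documents. No sample size, error rate or power figure is affected, because the plan has none.

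**What to change.** 1. In Protocol 7.1.2, limit the entry to preplanned or elective procedures where no untoward medical occurrence, meaning a condition that is new or has worsened since Baseline, led to the admission. This brings the causal part of the 7.1.1 qualifier into 7.1.2. A cut-off by planning date alone would be a poor substitute: it would bring under the hospitalization criterion later elective admissions that had nothing untoward behind them.
2. In the procedure bullet of 7.1.1, add *or if it has worsened since Baseline*, so that it agrees with the chronic-condition bullet above it.

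The cost is two phrases in the protocol, a few more SAE forms, and a slightly less favourable SAE count. No assessment or planned analysis changes.
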